11.1.2 Serious adverse event [SAE]

A Serious Adverse Event [SAE] is an AE that at any dose (including overdose):

- results in death;
- is life-threatening¹;
- requires inpatient hospitalisation or prolongation of existing hospitalisation²;

- results in persistent or significant disability or incapacity³;
- is a congenital anomaly or birth defect;
- is a medical important event⁴.

- 1 'Life-threatening' means that the subject is at immediate risk of death at the time of the SAE; it does not refer to an AE which hypothetically might have caused death if it were more severe.
- 2 Hospital inpatient admission (for more than one calendar day) or prolongation of a hospital stay by at least one calendar day are required for the treatment of the AE, or occurs as a consequence of the AE.

Hospitalisation does not include the following:

- Emergency room/ accident and emergency/ casualty department visits;
- Out-patient/ same-day/ ambulatory procedures;
- Observation/ short-stay units;
- Rehabilitation facilities/ health resorts;
- Hospice facilities;
- Respite care (e.g. caregiver relief);
- Skilled nursing facilities;
- Nursing homes;
- Custodial care facilities;
- Clinical research/ phase I units;
- Hospitalisation in the absence of a precipitating, clinical AE:
 - Admission for treatment of a pre-existing condition not associated with the development of a new AE or with worsening of a pre-existing condition (e.g. for work up of persistent pre-existing lab abnormality);
 - Social admission (e.g. patient has no place to sleep);
 - Administrative admission (e.g. for annual physical examination);
 - Optional admission not associated with a precipitating clinical adverse event (e.g. for elective cosmetic surgery).

- 3 'Persistent or significant disability or incapacity' means a permanent or significant and substantial disruption of a person's ability to carry out normal life functions. This definition is not intended to include experiences of relatively minor medical significance such as uncomplicated headache, nausea, vomiting, diarrhoea, influenza, and accidental trauma (e.g. sprained ankle) which may interfere or prevent everyday life functions, but do not constitute a substantial disruption.
- 4 Medical and scientific judgement should be exercised in deciding whether immediate reporting is appropriate in other situations where none of the serious criteria above are met. Important medical events that may not be immediately life-threatening or result in death or hospitalisation but may jeopardize the subject or may require intervention to prevent one of the other outcomes listed in the definition above should also usually be considered 'serious'. Examples of such events are intensive treatment in an emergency room or at home for allergic bronchospasm, blood dyscrasias, or convulsions that do not result in inpatient hospitalisation, or development of drug dependency or drug abuse.

Difference between 'severe' and 'serious'

The term 'severe' is often used to describe the intensity (severity) of an event (as in mild, moderate, or severe myocardial infarction). The event itself, however, may be of relatively minor medical significance (e.g. severe headache). This is not the same as 'serious', which is based on the outcome or action criteria usually associated with events that pose a threat to life or functioning. Seriousness (not severity) serves as a guide for defining regulatory reporting obligations.

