6.3 Description and rationale for conducting the trial

At present, there is minor evidence of using the phytoengineering-based drug product Imupret® in acute tonsillitis, pharyngitis and tonsillopharyngitis. The spectrum of its pharmacological properties includes antiviral, anti-inflammatory, and immunomodulatory action. The aggregate of these properties allows affecting almost all pathogenetic process links underlying the nosology in question, and favourable safety profile allows viewing Imupret as a basic therapeutic agent in treatment of non-bacterial forms of acute tonsillitis, pharyngitis, and tonsillopharyngitis. Our previous work showed that the use of Imupret in patients with non-bacterial tonsillitis accelerates regression of symptoms of tonsillitis and reduces the need for antibiotics. At the same time, there is a lack of studies, valid from the viewpoint of compliance with GCP standards have been conducted. Confirmation of high efficacy of Imupret in treatment of the above nosology group would be served as a justification for optimization of this nosology treatment scheme of delayed antibiotic prescription and recommendations for inclusion of this drug product into the national guidelines.

In the context of this clinical trial the two questions that are to be answered are:

1. Does Imupret®, taken during the diseases acute period help reduce the frequency of antibiotic use in children aged 6-12 ?
2. Does Imupret®, taken during the diseases acute period helps to accelerate the regression of symptoms in children aged 6-12?
3. Is the use of antibiotic delay technology safe for children aged 6-12 years?

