9.3 Exclusion criteria

- Score -1 to 3 according to Mclsaac Scale.
- Indication for hospitalization, including:
 - o purulent complications (peritonsillar abscess and others);
 - o severe general condition.
- Indication for immediate initiation of systemic antibiotic therapy
- patients at risk of developing severe complications, including e.g. clinically relevant concomitant diseases of heart, lungs, kidneys, liver, neuromuscular apparatus, cancer diseases, immunosuppression, diabetes mellitus, cystic fibrosis.
- suspected infectious mononucleosis (by clinical signs);
- use of systemic antibacterial or antifungal agents, systemic glucocorticosteroids, cytostatics, immunomodulatory drugs, "interferons" or interferon derivatives during the last 14 days prior to inclusion;
- presence of haemorrhagic or pronounced necrotic process in oral cavity or pharynx, including the lymphoid ring.
- Intolerability or individual hypersensitivity to any of the study drug ingredients and the reference treatment scheme.

Patients who refuse to sign the informed consent or who do not agree to passing on of their pseudonymous data to the monitor / CRO, the sponsor, and competent national or European community authorities must not be included in this trial.

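### Footnote 2 to the SAE definition sets a minimum length of stay, so a same-day inpatient admission for a tonsillitis complication is not automatically an SAE

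*Protocol*

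**What the plan says.** Protocol section 11.1.2 lists, among the seriousness criteria, an event that "requires inpatient hospitalisation or prolongation of existing hospitalisation". The criterion itself names no length of stay. Footnote 2 supplies one: "Hospital inpatient admission (for more than one calendar day) or prolongation of a hospital stay by at least one calendar day". The list under the footnote then says what is not hospitalisation, including "Emergency room/ accident and emergency/ casualty department visits", same-day procedures and "Observation/ short-stay units".

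Footnote 4 leaves another route. It covers "Important medical events that may not be immediately life-threatening or result in death or hospitalisation but may jeopardize the subject", or that may need intervention to prevent a listed outcome. Such events "should also usually be considered 'serious", subject to medical and scientific judgement.

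Four other places bear on the point:

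- Section 6.3, question 3, asks: "Is the use of antibiotic delay technology safe for children aged 6-12 years".
- Section 11.1.1 defines an AE for a subject who has been given the IMP, and generally keeps worsening symptoms and other expected outcomes of the disease out of AE recording.
- Section 11.1.4 sets no alert terms.
- Section 12.2.4 and the SAP safety evaluation tabulate AEs by frequency, intensity, relationship, outcome and seriousness. Neither has a tabulation of hospital admissions.

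**The concern.** The harm one would most want to see in a trial of delayed antibiotics is a complication that needs hospital care. In an open-label trial, admission to hospital is a comparatively objective marker of it. Footnote 2 removes the shortest admissions from that marker and leaves their classification to judgement, and section 8.4 confirms that there is no blinding.

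At stake are the SAE label and the 24-hour report to the ethics committee and authority under section 11.4. With no alert terms, that route carries only SAEs. The descriptive safety statement is also affected: with few events, whether one or two admissions count as SAEs can decide whether an arm is reported as having none. Efficacy analyses and the sample size are not touched.

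**Working it through.** The plan gives no figure on this point, so there is nothing to reproduce. The check is to take one case through the rules: a child admitted as an inpatient for a purulent complication and discharged the same day.

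1. **Is it an AE (11.1.1)?** Not certain. A new illness is an AE, but expected outcomes of the disease under study are generally not recorded, and the protocol does not say whether a purulent complication is one of these. The definition also refers to subjects given the IMP, while the reference arm receives no Imupret. Read literally, it does not cover that arm.
2. **Does it meet the hospitalisation criterion (11.1.2)?** The criterion alone would say yes. Footnote 2 says no, because the stay did not exceed one calendar day.
3. **Does it meet another criterion?** Only if it is, for example, life-threatening or disabling.
4. **Is it an important medical event (footnote 4)?** Possibly. This rests on judgement, and the wording is that such events are usually, not always, serious. The footnote's examples (bronchospasm, blood dyscrasias, convulsions, drug dependency or abuse) include no tonsillitis complication.
5. **Does it reach expedited reporting (11.4)?** Only if step 3 or 4 made it an SAE, since 11.1.4 adds nothing.
6. **Does it appear in a table (12.2.4, SAP safety evaluation)?** If recorded as an AE, yes, but not as an admission.

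**A single overnight stay** can be read in two ways. It touches two calendar dates, so it may exceed one calendar day and qualify. Counted as elapsed time, one night is no more than one day and does not qualify. The protocol does not choose, so sites could classify the same stay differently.

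**Illustration of scale.** Inputs: n = 100 per arm (section 8.2) and x = 0, 1 or 2 events (assumed, because the documents give no admission rate). The exact two-sided 95% upper limit is the 0.975 quantile of a Beta(x + 1, n − x) distribution. For x = 0 this reduces to 1 − 0.025^(1/100) = 0.0362.

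| Events in 100 | Upper 95% limit |
|---|---|
| 0 | 3.6% |
| 1 | 5.4% |
| 2 | 7.0% |

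One event more or less at these counts moves the limit by 5.4 − 3.6 = 1.8 or 7.0 − 5.4 = 1.6 percentage points. This shows how sensitive the statement is to single events. It does not estimate how many would be missed.

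**The case against.** The strongest reply is that footnote 2 governs seriousness, not recording. Section 11.3 requires every AE, serious or not, to be documented, and the AE tables include non-serious events. That stands: what is at risk is the SAE label and the expedited report, not necessarily the record.

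A second reply is that an SAE must first be an AE, so section 11.1.1 may be the larger obstacle. If a complication is left out there, changing footnote 2 does not bring it back. That also stands, and the two sections have to be changed together.

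A third is that the trial is exploratory, safety is descriptive, and both arms follow the delayed-prescription approach, so there is no immediate-antibiotic comparator for question 3. This limits what any SAE count can show. It does not explain why brief admissions should be classified by judgement.

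A reader might infer more than the documents support:

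- **That brief admissions cannot be SAEs.** Footnote 4 and the other criteria can still make them so.
- **That SAE counts will fall by a given fraction.** This needs an admission rate, a share of short stays and an assumption that footnote 4 captures none of them. The documents support none of the three.
- **That the footnote is inconsistent in treating one added day as serious but not a one-day admission.** If an overnight stay qualifies, the two limits agree.
- **That section 9.3 contradicts the footnote.** Its entry "Indication for hospitalization, including" purulent complications is an eligibility rule. It does not define seriousness and is silent on length of stay.
- **That every observation-unit contact should be an SAE.** That is one possible convention, and leaving such contacts out is not an error.

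**Conclusion.** The point holds in a limited form. Footnote 2 narrows a criterion that otherwise has no length limit. A same-day inpatient admission for a tonsillitis complication, and on one reading a single overnight stay, is therefore an SAE only through another criterion or the judgement of an unblinded investigator. It may still appear as a non-serious AE, unless section 11.1.1 keeps it out.

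The size is unknown, because the documents give no rate of complications or admissions. The limits for an arm of 100 are illustrative and rest on assumed counts. The change should be made because it is cheap and bears directly on question 3 of section 6.3. It does not alter the efficacy conclusions.

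**What to change.** Four changes, all to reporting and none to clinical management:

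1. In footnote 2 of section 11.1.2, delete the parenthetical length limit on admissions. This also removes the ambiguity about overnight stays.
2. Reconcile sections 11.1.1 and 11.1.2 so that complications of tonsillitis leading to hospital care are recorded as AEs in both arms, including the reference arm, which receives no IMP.
3. Record admission and discharge dates in the CRF.
4. In section 12.2.4 and the SAP safety evaluation, tabulate hospital admissions of any length by arm, including stays in short-stay or observation units.

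Short-stay and observation contacts need not be classed as SAEs; the table is enough to make them visible. The cost is a few lines of protocol wording, two CRF dates, one table and possibly a few more SAE reports.

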11.1.3 Adverse reactions [AR]

An adverse reaction [AR] is any noxious and unintended response to an IMP irrespective of the dose administered. The phrase 'response to an IMP' means that a causal relationship between

the administration of the IMP and the occurrence of an AE is at least a reasonable possibility (refer to section 11.3).

All AEs will be judged by either the investigator or the sponsor as 'related' or 'not related' to the IMP.

An unexpected AR is an AR for which the nature or severity is not consistent with the applicable reference safety information for the Imupret® or Reference treatment provided in the Summaries of Product Characteristics.

When an unexpected AR also meets the definition of a SAE (refer to section 11.1.2), it is considered an unexpected serious AR. The co-ordinating investigator will report all suspected unexpected serious adverse reactions [SUSAR] to competent authorities, ethic committees, investigational sites, Bionorica SE as the supporter of this trial and other relevant recipients in all participating countries, in accordance with applicable reporting requirements.

11.1.4 Alert terms and other reasons for expedited reporting to Pharmacovigilance

No special events are to be reported as alert terms in this trial.

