9.2 Inclusion criteria

- Children (males/females), 6 - 12 years old, with severe acute tonsillitis.
- Possibility to initiate therapy within 72 hours since the onset of the disease symptoms.
- Score 4-5 according to Mclsaac Scale.
- Patient's and (or) one of his/her parents' willingness and ability to fulfil the requirements of the Study Protocol.
- Signed informed consent of the patient and (or) his/her parents for participation in the study.

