9.4.3 Premature termination of the trial

Premature termination of a clinical trial may occur upon decision of the sponsor, the Principal Investigator, by request of an authority or because of withdrawal of positive vote by the responsible ethics committee. Furthermore, the Principal Investigator / sponsor has the right to close participating center(s) of the trial, at any time, although this can occur only after consultation between involved parties.

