11.4 Reporting of SAE

Any SAE and AE that fulfil a reason for immediate reporting (as defined in section 11.1.4) will be reported immediately (within 24 hours after receipt) to the responsible ethics committee and authority according to the obligations of the Ukraine (online to State Expert Center MH).

Moreover, within 15 days after receipt by the investigator via telephone, fax or e-mail to the Drug Safety department of Bionorica SE:

Bionorica SE
Drug Safety
[contact]
[contact]
E-mail: [contact]

The initial report must be as complete as possible. The report should include at least the following information:

- **Clinical trial subject identification** (e.g. assigned subject number, age or year of birth, gender)
- **Identifiable reporting source** (e.g. centre number, name of investigator, telephone number, fax and/ or e-mail address)
- **Identification of the clinical trial** (e.g. trial code) or IMP
- **SAE term** (preferably: diagnosis; if possible, also including description and course of the SAE)
- **Seriousness criterion** (refer to section 11.1.2)
- **Causal relationship** between the occurrence of an AE and the administration of the IMP as assessed by the investigator according to the available data as defined in 10.2. If based on follow-up information the investigator changes his/her initial causality assessment, this should be submitted to the Drug Safety department of Bionorica SE immediately (i.e. within 24 hours after receipt) by using the SAE report form.
- **Signature of the investigator**

Following a report by phone, written information has to be sent by fax or e-mail to the Drug Safety department of Bionorica SE within two working days. When necessary an 'SAE Report Form' will be accompanied by relevant pages from the CRF, e.g. for medical history, AEs or concomitant medication (online-form in official site of State Expert Centre MH).

If the investigator does not have all information regarding an SAE, he/she will not wait to receive additional information before notifying the sponsor of the event and completing the 'SAE report form'. Information not available at the time of the initial report (e.g. an end date for the SAE or laboratory values received after the report) will be documented on a follow-up 'SAE report form' and reported within 15 days after receipt to the Drug Safety department of Bionorica SE.

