12.2 Statistical evaluation

The statistical planning of the trial and the statistical analyses will be conducted following the principles specified in the ICH Topic E9 (ICH, 1998), and will be carried out by a qualified statistician in accordance with the ICH. Technical details of the statistical analyses will be specified prior to data analyses.

In general, there will be one main statistical evaluation.

Data base will be closed after all data are entered and cleaned.

In general, unless otherwise stated, continuous data will be summarized by means of descriptive statistics (mean, standard deviation (SD), median, quartiles, minimum, and maximum). Categorical variables will be described in contingency tables as absolute number and percentages.

AEs will be evaluated considering frequency and intensity. Furthermore, AEs will be evaluated considering relationship to the IMP, outcome, and seriousness. Both will be described by absolute and relative frequency. Descriptive statistics will be calculated for clinical laboratory parameters determined. Frequencies of values inside and out of normal range (i.e. above and below) will be given where possible.

This is an exploratory trial with no formal sample size estimation. Therefore, beneath descriptive statistics of efficacy endpoints, concluding statistics may be performed in a data driven way, in order to find clinically relevant differences between study participants, time points and treatments. Possible corrections to prevent an alpha inflation will be performed, if meaningful.

Specifications of the biometrical evaluation will be defined after all data management processes of the study phase will be terminated and data base was closed. In general, variables will be analyzed considering the underlying analysis set, treatment and time point, if meaningful.

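### A complication of tonsillitis managed without admission may be neither recorded as an AE nor expedited, and no stated event obliges a cumulative safety review

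*Protocol*

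**What the plan says.** Protocol Section 6.3 lists as its third question: "Is the use of antibiotic delay technology safe for children aged 6-12 years". Section 9.2 admits only children with "Score 4-5 according to Mclsaac Scale". The table in Section 6.1 gives about a 50% probability of streptococcus at that score, and Section 10.6 gives 51-53% at score 4. In both arms the decision on antibiotics is deferred to the status visit on day 3.

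The safety sections then say the following.

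- **Section 11.1.1 (AE):** worsening of common symptoms and expected outcomes of the disease are, as a rule, not recorded as AEs. The definition also refers to subjects who have received the IMP.
- **Section 11.1.2 (SAE):** hospitalisation means an inpatient stay of more than one calendar day. Emergency-room visits, observation or short-stay units and "Out-patient/ same-day/ ambulatory procedures" do not count. A further clause says that important medical events not leading to admission should usually be treated as serious.
- **Section 11.1.4 (alert terms):** "No special events are to be reported as alert terms in this trial".
- **Section 11.4 (reporting):** the 24-hour report to the ethics committee and authority begins "Any SAE and AE that fulfil a reason for immediate reporting (as defined in section 11.1.4".
- **Section 9.4.3 (termination):** "Premature termination of a clinical trial may occur upon decision of the sponsor, the Principal Investigator". An authority's request or a withdrawn ethics vote can also end the trial. No triggering event is named.
- **Section 12.2 and the SAP:** "In general, there will be one main statistical evaluation".

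**The concern.** Section 11.4 already has a fast route for AEs that matter but are not serious. It depends on a list in Section 11.1.4, and that list is empty, so only SAEs travel within 24 hours. One step earlier, Section 11.1.1 may stop a complication of tonsillitis from being recorded as an AE at all, in which case the seriousness test is never applied to it.

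Two things are at stake. One is safety oversight: Section 9.4.3 allows early termination but links it to no count or review. The other is the answer to question 3. A low count of complications is informative only if every complication was recorded, in both arms and by the same rule.

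**Working it through.** **Path of an on-trial purulent complication.** The plan states no complication rate, alert count or review threshold, so there is no figure of its own to reproduce. The route through the clauses is as follows.

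1. *Is it an AE?* Section 11.1.1 points both ways. A new illness is an AE; an expected outcome of the disease generally is not. The text does not say which applies to, for example, a peritonsillar abscess. Read literally, the definition also covers only children given the IMP, and reference-arm children receive no Imupret (Section 8.3.3). Section 11.2 collects AEs from consent onward, which suggests that both arms are meant.
2. *Is it an SAE?* If the child is admitted for more than one calendar day, yes. Section 9.3 lists purulent complications under indications for hospitalisation, so this should be the usual path. If the child is not admitted, the important-medical-event clause usually makes it serious, but this rests on judgement, and none of the clause's examples is a purulent complication.
3. *If it is an AE but not judged serious, is it expedited?* No, because Section 11.1.4 is empty.
4. *Does any number of such events oblige a review?* None is stated in the text available.

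**Timing conflict.** Section 11.3 has the SAE form sent at once to the Drug Safety department. Section 11.4 allows 15 days for notice to the same department. The two must be reconciled.

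**Scale, under assumed rates.** Inputs are N = 200 (Section 8.2) and a complication rate p of 0.5% to 5%, which is an assumption. The expected number is 200p. For illustration only, let a review be triggered by the third event:

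P(X ≥ 3) = 1 − [(1−p)^n + n·p·(1−p)^(n−1) + (n(n−1)/2)·p²·(1−p)^(n−2)]

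- p = 0.5%, n = 200: 1 − (0.367 + 0.369 + 0.184) = 0.080
- p = 1%, n = 200: 1 − (0.134 + 0.271 + 0.272) = 0.323

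| Assumed rate | Expected in 200 | P(≥3 in 200) | P(≥3 in first 100) |
|---|---|---|---|
| 0.5% | 1 | 0.080 | 0.014 |
| 1% | 2 | 0.323 | 0.079 |
| 2% | 4 | 0.765 | 0.323 |
| 3% | 6 | 0.941 | 0.580 |
| 5% | 10 | 0.998 | 0.882 |

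These figures cover all complications, not the subset that is neither admitted nor judged important. The documents give nothing from which to size that subset; 200p is only its ceiling. The last column also assumes that events are known as they occur, whereas follow-up runs to day 28.

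**What a clean record would show.** With no events, the one-sided 95% upper bound is 1 − 0.05^(1/200) = 1.5% for the whole trial and 1 − 0.05^(1/100) = 3.0% for one arm. Both bounds hold only if no complication was left unrecorded.

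**The case against.** The harms that matter most are largely covered. The protocol's own classification points a purulent complication or severe general condition towards admission, hence an SAE and a 24-hour report. The important-medical-event clause sets a default for non-admitted cases, and one of its examples is allergic bronchospasm treated at home or in an emergency room. Section 9.3 excludes children who need antibiotics at once or are at risk of severe complications. Section 6.1 limits the delay to 36-48 hours, and Section 8.5 allows unscheduled visits on worsening. The authority and ethics committee receive each SAE and can end the trial. Section 11.4 also has the sponsor notify other important safety issues. The trial is open-label, so investigators see arm and event together. An empty alert list for a marketed non-prescription product can be a deliberate choice.

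Most of this stands, and it narrows the point. But each safeguard works case by case, and most rest on judgement. None settles whether Section 11.1.1 removes a disease complication from AE recording, and none obliges anyone to look at the accumulated count.

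A reader might infer that a run of abscesses would go unseen until the final analysis, or that the trial has no safety oversight. The documents do not support either. The sentence on one main evaluation concerns statistical analysis. Section 3, on administrative structure, was not available, so a safety body named there cannot be excluded, although the abbreviation list contains none.

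**Conclusion.** The point holds in a limited form. Most purulent complications should reach the authority and ethics committee as SAEs. The gap concerns a complication treated without admission and regarded as a disease outcome, which could go unrecorded or unexpedited, together with the absence, in the supplied text, of any event that obliges a cumulative review.

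Its size cannot be computed from the documents. Under the assumed 0.5% to 5%, 1 to 10 complications of all kinds would be expected in 200 children, and an unknown share would fall in the gap.

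A reader might also expect a count by arm to show whether delayed antibiotics are as safe as immediate ones. It cannot, because both arms delay antibiotics. The count would serve safety oversight and complete description only.

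**What to change.** 1. **Section 11.1.4.** Replace the present sentence with alert terms taken from the protocol's own text: purulent complication, including peritonsillar abscess; severe general condition or a new indication for hospitalisation (both from Section 9.3); allergic reaction with dyspnoea (Section 10.9.2).
2. **Recording.** State that these terms are recorded as AEs in both arms, notwithstanding the disease-outcome exception in Section 11.1.1, and go by the Section 11.4 route whether or not they are judged serious. An alert list without this statement would not be enough, because Section 11.4 acts only on events already recorded as AEs.
3. **Reconciliation.** Bring Sections 11.1.1, 11.1.2 (important medical events) and 11.1.4 into line for complications of the disease. Reconcile Sections 11.3 and 11.4 on the time limit for notice to Drug Safety.
4. **Count.** Have existing staff keep a running count of these terms by arm. When it reaches a number that the sponsor fixes before the first patient enters, a review is held and documented. Leave antibiotic prescription and lack of effect out of the count, so that it does not become a look at efficacy.

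No stopping or treatment rule is proposed, and no new committee is needed.

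The cost is a few sentences, a tally, some extra expedited reports and an occasional unnecessary review. With the illustrative trigger of three, a review would occur in 8% of trials at 0.5% and 32% at 1%. The documents do not say whether 1% would be unusual, so the sponsor should choose the number with its own expected rate in view.
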